6.4 Method of statistical analysis

No formal statistical hypothesis testing will be performed on the data from this study.

All safety, tolerability, pharmacokinetic, pharmacodynamic and efficacy data relating to each dose level will be listed and summarized as detailed below.

6.4.1 Safety Data

Safety data will not be formally analysed. All patients who receive at least one dose of AZD8330 will be included in the assessment of AE profile (evaluable for safety population). Other safety data will be assessed in terms of clinical chemistry, haematology, urinalysis, vital signs, MUGA scan/Echocardiogram, ECGs, ophthalmologic examination, and O₂ saturation. At the end of the study, appropriate summaries of all safety data will be produced, as defined below and in the SAP.

Data from all cycles of initially randomised treatment will be combined in the presentation of safety data. AEs will be listed individually by patient and dose group. For patients who have a dose modification, all AEs (due to drug or otherwise) will be assigned to the initial dose

group. The number of patients experiencing each AE will be summarised MedDRA system organ class (SOC), MedDRA preferred term (PT) and CTC grade. The number and % of patients with adverse events in different categories (e.g. causally related, CTC grade ≥ 3 etc) will be summarised by dose group, and events in each category will be further summarised by MedDRA SOC and PT, by dose group.

Any AE occurring before treatment (ie, before study Day 1) will be included in the data listings but will not be included in the summary tables of adverse events. In addition, a separate data listing of pre-treatment AEs will be produced.

Any AE occurring within 30 days of treatment withdrawal will be included in the AE summaries. Any events in this period that occur after a patient has received further therapy for cancer (following withdrawal of study medication) will be flagged in the data listings. AEs occurring more than 30 days after withdrawal of study medication will be listed separately, but not included in the summaries.

Clinical chemistry, haematology, urinalysis, vital signs, MUGA scan/Echocardiogram, ECGs, ophthalmologic examination, and O₂ saturations will be listed individually by patient and dose group and summarised by treatment dose, as follows:

Haematology, clinical chemistry, vital signs and ECG data will be suitably summarised by dose level for all patients by:

- summary statistics of observed values: mean, standard deviation, minimum, maximum, n
- summary statistics of change from baseline values: mean, standard deviation, minimum, maximum, n
- Individual patient listings: including highlighting of haematology and clinical chemistry values outside the local laboratory reference ranges

Qualitative assessments will be summarised for all subjects using the number of subjects with results of negative, trace or positive.

Graphical presentations of safety data will be presented as is deemed appropriate.

6.4.2 PK data

The concentration-time profiles of AZD8330 and any known major active metabolites, along with the derived pharmacokinetic variables, will be listed for each patient per dose and dosing day and summarised appropriately, as described below:

The following parameters will be reported for day 1 and day 15 if the data allow:

Summaries of AUC_{0-t} , $AUC_{0-\tau}$, C_{max} , C_{min} , CL/F and V_z/F will contain:

- the geometric mean (gmean, calculated as $\exp(\mu)$, where μ is the mean of the data on a log scale)
- coefficient of variation (CV, calculated as $100 \times \sqrt{\exp(s^2)-1}$, where s is the standard deviation of the data on a log scale)
- arithmetic mean, standard deviation (calculated using untransformed data)
- median, minimum, maximum
- number of observations (n).

Summaries of $t_{1/2}$ and λ_z will present:

- arithmetic mean and standard deviation
- median, minimum, maximum, n.

Summaries of t_{max} will present:

- median, minimum, maximum, n.

Summaries of plasma concentration-time data will present:

- gmean and CV
- $\text{gmean} \pm \text{standard deviation}$ (calculated as the exponential of the mean \pm standard deviation on the log scale)
- arithmetic mean, standard deviation (calculated using untransformed data)
- median, minimum, maximum, n.

The following figures will be produced to present the pharmacokinetic data:

- Concentration-time profile plots for each patient (linear concentration scale), showing overlapping profiles for 0-48h for all days on which PK samples are available as separate lines.
- Concentration-time profile plots for each patient (log concentration scale), showing overlapping profiles for 0-48h for all days on which PK samples are available as separate lines.
- Concentration-time profile plots for each patient (linear concentration scale), showing a single profile for the entire dosing period.

- Concentration-time profile plots for each patient (log concentration scale), showing a single profile for the entire dosing period.
- Gmean +/- standard deviation (one line for each dose level, linear concentration scale)
- Gmean +/- standard deviation (one line for each dose level, log concentration scale)
- Dose-normalised C_{\max} and AUC versus dose

Additional or alternative plots may be constructed as deemed appropriate based on emerging data.

Non-quantifiable (NQ) values of plasma concentrations will be handled as follows:

- if, at a given time point, 50% or less of the plasma concentrations are non-quantifiable (NQ), the gmean, CV, gmean \pm standard deviation, arithmetic mean and standard deviation will be calculated by substituting the limit of quantification (LOQ) for values which are NQ.
- if more than 50%, but not all, of the concentrations are NQ, the gmean, CV, gmean \pm standard deviation, arithmetic mean and standard deviation will be reported as not calculable (NC)
- if all the concentrations are NQ, the gmean and arithmetic mean will be reported as NQ and the CV, gmean \pm standard deviation and standard deviation as NC
- if the calculation of the gmean – standard deviation results in a value less than the LOQ, NQ will be displayed.

6.4.3 Pharmacodynamic data

6.4.3.1 PBMC biomarkers

The levels of biomarker pERK in PBMCs, and their baseline scaled ratios (BSRs), defined as post-dose \div pre-dose, will be listed and summarised by dose group.

If the data are suitable the extent of pERK inhibition in PBMCs following the oral doses in this study will be investigated in all patients with pre and post dose samples using graphical means, including scatter plots of the following for each biomarker:

- BSR vs dose group
- BSR vs pre-dose biomarker level

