4.4.4 Phospho-ERK in PBMCs

4.4.4.1 Methods of assessment

The level of ERK phosphorylation (pERK) will be assessed in PBMCs by measuring phorbol ester (TPA) stimulated pERK production, using specific antibodies and flow cytometry.

All patients will contribute blood samples for PBMC preparation at each of the following time points:

- Day 1: Pre-dose, 30 minutes, 1 hour 30 minutes, 4, 8 and 24 hours

At each time point 2 x 2mL of blood will be drawn for PBMC analysis. Drawn samples will be immediately processed, stored and then shipped as detailed in the Laboratory Handbook for Investigators. Samples will be shipped initially to the coordinating laboratory, and subsequently sent for analysis to a referral laboratory.

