6.5 Determination of sample size

Part A of the study is not formally powered but is designed to provide adequate tolerability, safety, pharmacokinetic, and pharmacodynamic data.

Part A is also designed to ensure at least 6 evaluable patients are recruited at the dose deemed to be MTD.

The number of patients has been based on both feasibility and obtaining adequate data to assess the biological activity of AZD8330 in tumour in terms of the biomarker pERK in tumour, based on average within-patient reduction in pERK from baseline, as measured using semi-quantitative IHC methods.

Average reductions of 83% on pERK were observed in the first in man study with the MEK inhibitor AZD6244 ([Adjei A et al 2006](#)). The within patient standard deviation of the change from baseline (on the log scale) from this study is estimated as 2.2. 10 patients would therefore provide 80% power to detect an average 70% reduction at the 1-sided 20% significance level.

Therefore approximately 10 evaluable patients at each dose level are considered reasonable to indicate the possibility of biological activity.

The expansion also provides an opportunity to provide a better estimate of the tolerability of each dose for onward development. Expanding the cohort at the maximum tolerated dose from the dose escalation to around 20 provides a stronger estimate of the true DLT rate. For example if the MTD cohort had only 6 patients then:

- If 0 out of 6 DLTs are observed it can be concluded that the true DLT rate is less than 30% with 90% confidence.
- If 1 DLT (16.7%) is observed it can be concluded that the true DLT rate is less than 50% with 90% confidence.

However, with an additional 18 evaluable patients for example:

- If 0 out of 24 DLTs are observed it can be concluded that the true DLT rate is less than 10% with 90% confidence.
- If 4 out of 24 DLTs (16.7%) are observed it can be concluded that the true DLT rate is less than 32% with 90% confidence.

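### Plotting post/pre pERK ratio against the pre-dose value that forms its denominator tends to give a negative slope from noise alone (minor)

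*Protocol*

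**What the plan says.** Protocol section 6.4.3.1 says that pERK levels "and their baseline scaled ratios (BSRs), defined as post-dose" divided by pre-dose, will be listed and summarised by dose group. If the data are suitable, the extent of inhibition "will be investigated in all patients with pre and post dose samples using graphical means". Two scatter plots are named: BSR against dose group, and "BSR vs pre-dose biomarker level".

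Section 4.4.4.1 gives the sampling times: "Day 1: Pre-dose, 30 minutes, 1 hour 30 minutes, 4, 8 and 24 hours". That is one pre-dose time point and five post-dose time points, measured by TPA-stimulated flow cytometry.

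The effect on pERK in PBMCs is a secondary objective (section 2.2). Section 6.4 states: "No formal statistical hypothesis testing will be performed on the data from this study". Section 6.4.3.1 gives no scale for the plot and no caution about the shared pre-dose value.

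**The concern.** A patient whose single pre-dose reading is high by chance moves to the right on the x-axis and, because that reading is the denominator, down on the y-axis. A reading that is low by chance does the reverse. The cloud of points tilts downward with no biology behind it. All five post-dose ratios of a patient share the same denominator, so looking at several post-dose times does not remove the effect.

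With no test planned, a reader interprets the picture directly. A downward tilt invites the view that patients with high baseline pERK are inhibited more. Section 6.4.3.2 also plots change in lesion length against pre-dose biomarker level and against BSR, so both quantities are already looked at as possible explanatory variables.

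**Working it through.** **The plan's own pERK figure.** Section 6.5 states: "The within patient standard deviation of the change from baseline (on the log scale) from this study is estimated as 2.2", and "10 patients would therefore provide 80% power to detect an average 70% reduction at the 1-sided 20% significance level". On the natural-log scale the effect is |ln 0.3| = 1.204. Then n = (2.2 × (0.842 + 0.842) / 1.204)² = 9.46, so 10. Power at n = 10 is 81.3% (normal) or 80.3% (noncentral t), so the stated 80% reproduces. The figure concerns tumour pERK by immunohistochemistry with another MEK inhibitor. It does not set the noise of the PBMC assay.

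**Model in which baseline has no effect.** For each patient:

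- log pre = b + e1
- log post = b + d + e2
- b is the patient's true level (between-patient SD sb)
- e1 and e2 are independent errors (within-patient SD sw)
- d is the log inhibition effect, independent of b

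Then log BSR = d + e2 − e1. Its covariance with log pre is −sw², and the variance of log pre is sb² + sw², so:

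- expected slope of log BSR on log pre = −sw² / (sb² + sw²)
- correlation, if d is the same for all = −sw / √(2(sb² + sw²))

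The slope does not contain n, so more patients do not remove it. It also does not depend on how much d varies between patients.

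**Results.** The protocol gives neither SD for PBMCs; both are assumed.

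| sw | slope at sb = 0.3 | slope at sb = 1.0 |
|---|---|---|
| 0.1 | −0.01/0.10 = −0.10 | −0.01/1.01 = −0.01 |
| 0.2 | −0.04/0.13 = −0.31 | −0.04/1.04 = −0.04 |
| 0.3 | −0.09/0.18 = −0.50 | −0.09/1.09 = −0.08 |
| 0.5 | −0.25/0.34 = −0.74 | −0.25/1.25 = −0.20 |

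**A middle case: sw = 0.3, sb = 0.5.** The slope is −0.09/0.34 = −0.26 and the correlation −0.36. In 20,000 simulated data sets of 10 patients with constant inhibition:

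- 86% sloped downward.
- The mean rank correlation was −0.32. Ranks do not depend on whether the axes are logged.
- The geometric mean BSR in the higher-baseline half was 0.80 times that in the lower half. If true BSR is 0.30 for everyone, the halves show about 0.30 × √0.80 = 0.27 and 0.30 / √0.80 = 0.34.

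**Checking the alternatives, same middle case.**

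- *Log post against log pre.* Slope = sb² / (sb² + sw²) = 0.25/0.34 = 0.74, where strictly proportional inhibition without noise gives 1. This is the same picture sheared, since 0.74 = 1 − 0.26, so it still needs a caution.
- *Log BSR against the mean of log pre and log post.* With SD of d equal to sd, slope = (sd²/2) / (sb² + sd²/4 + sw²/2). At sd = 0 it is 0.00. At sd = 0.15 it is 0.011/0.301 = +0.04. At 0.3 it is 0.045/0.318 = +0.14. At 0.6 it is 0.18/0.385 = +0.47. It is near neutral only when inhibition varies little among the patients plotted.

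**The case against.** The strongest reply is that little hangs on this plot. It is one of two named plots in an open list, made only if the data are suitable. pERK levels and BSRs are also listed and summarised by dose group, and section 3.2.2 reports a population PK/PD model of pERK. The escalation criteria in section 3.1.4.1 do not use pERK. BSR by dose group does not put the pre-dose value on both axes. All of this stands, and it limits the consequence.

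Three stronger readings are tempting, and the protocol does not support them:

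- *That these plots are the whole analysis of the pERK objective.* The listings and summaries by dose group show otherwise.
- *That the plan makes a predictive-marker claim.* It states no hypothesis about baseline pERK. The misreading is a risk for a reader and is not asserted in the text.
- *That the artefact is known to be large.* Applying the SD of 2.2 to PBMCs (sw = 2.2/√2 = 1.56) would give slopes of −0.71 to −0.96, but that SD belongs to tumour tissue and another drug. A correlation of −0.71, from equal variances and unrelated pre- and post-dose values, is no better. If true post-dose level is unrelated to true baseline, fractional inhibition really does rise with baseline, so the association is not spurious.

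It can also be said that a caution could be left to a later document. Section 6.1 says no separate analysis plan will be prepared, although section 6.4.1 refers to one, so the protocol is the safer place.

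**Conclusion.** The point holds and is minor. The planned plot shares one noisy value between its axes, so its expected slope is below zero when inhibition is unrelated to baseline. The built-in slope is between about −0.01 and −0.74 on the log scale for the assumed SDs, and −0.26 in the middle case. These figures rest on independent errors of equal size before and after dosing, and on noise levels that the protocol does not state. The slope would vanish only if the pre-dose value carried no measurement or within-patient noise, which is unlikely for one stimulated flow-cytometry time point. A downward slope is a tendency and not a certainty: in the middle case 14% of data sets of 10 patients do not show it. Neither dose escalation nor the plot of BSR by dose group is touched by this coupling.

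**What to change.** In section 6.4.3.1, replace the BSR-against-pre-dose plot with log post-dose against log pre-dose pERK. Mark points by dose group and add a no-change line and lines of constant percentage inhibition. State beside it that a slope below 1 is expected from noise in the pre-dose value and is not evidence that baseline pERK predicts inhibition.

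If a change-against-level plot is wanted, draw log BSR against the mean of log pre and log post within each dose group. Do not pool it across doses: section 3.2.2 reports data from 0.5 to 60 mg, and dose-driven spread in inhibition biases that form upwards.

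Keep BSR by dose group as planned. The cost is a changed axis and one sentence, with no new samples or data.

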6.4.3.2 Tumour response

Summaries of best overall response and Objective Response Rate by initial treatment will be produced, for all patients from the safety population who have a baseline RECIST assessment and at least one follow-up RECIST assessment.

Graphical presentations including the following will be produced:

Waterfall plots for each dose level showing the sum of the changes in target lesions for each patient at week 8 compared to baseline, indicating tumour type for each patient.

Scatter plots of change in lesion length vs pre-dose biomarker levels

Scatter plots of change in lesion length vs biomarker BSR

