2.3 Exploratory objectives

Exploratory objectives	Outcome variables
To obtain a preliminary assessment of efficacy of AZD8330	Objective Response Rate (ORR; based on RECIST) for patients with measurable disease Best Overall Response (BOR; based on RECIST) for patients with measurable disease Patients with non target disease will be assessed for complete response, stable disease or progression

To collect a blood sample (optional) for DNA extraction and storage to investigate whether variability in the AZD8330 PK, safety, efficacy or pharmacodynamic results could be explained by differences in the patient's genotype

Correlation of host polymorphisms with variation in PK, safety or response parameters observed in patients treated with AZD8330

^a BNP or NT-proBNP are permitted in the protocol, however these shall be collectively referred to as BNP for the remainder of the protocol.

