4.4 Efficacy and pharmacodynamic measurement and variables

4.4.1 Tumour assessment by imaging techniques using RECIST

The RECIST guidelines for measurable, non-measurable, target and non-target lesions, and the objective tumour response criteria (complete response (CR), partial response (PR), Stable disease (SD) or progression of disease (PD)) are presented in [Appendix C](#). The RECIST criteria will be used to programmatically determine ORR. Patients with non-measurable disease only will be assessed according to RECIST criteria for non-target and new lesions in [Appendix C](#).

Baseline tumour assessments should be performed no more than 4 weeks before the start of study treatment, but should be as close as possible to the start of study treatment. Following date of the first dose with AZD8330, efficacy for all patients will be assessed by objective tumour response every 8 weeks thereafter relative to the date of the first dose with AZD8330. Assessments may be performed +/- 7 days relative to the specified visit date. In addition, patients who progress between scheduled visits should have a radiological imaging for confirmation.

Baseline radiological examination, preferably contrast enhanced CT, will be performed on anatomical coverage to adequately define all areas of disease. Post-baseline imaging should follow and evaluate all lesions identified at baseline. MRI should only be used where CT is not feasible or it is medically contra-indicated.

For patients with measurable lesions, all measurable lesions confirmed and assessed by radiological methods (CT or MRI scans) up to a maximum of 5 lesions per organ and 10 lesions in total, representative of all involved organs, should be identified as target lesions, recorded and measured at baseline, and at the time points specified above.

Non-target lesions will also be monitored throughout the study, and an assessment of non-target lesions will be made and recorded as “present”, “present with progression” or “absent”. Details of any new lesions will also be collected.

If an unscheduled radiological and clinical tumour assessment is performed, and the patient has not progressed, the next scheduled tumour assessment should still be performed at the planned time (as detailed in the study plan) relative to date of first dose of AZD8330.

Tumour assessment will be performed in accordance with the protocol schedule until evidence of one of the following:

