- Progression of disease (patients will be followed for subsequent therapy and survival)
- Death without evidence of progression
- Withdrawal of consent
- Withdrawal from treatment

If a patient has any palliative radiotherapy to a lesion that lesion should not be included in assessment of response, but should be assessed for progression.

A patient will be determined to have progressed if they have progression of target lesions, clear progression of existing non-target lesions, or the appearance of one or more new lesions. Death will be regarded as a progression event in those patients who die before disease progression. Unequivocal malignant disease not identified prior to starting study treatment on additional anatomical imaging (e.g., computed tomography (CT), magnetic resonance imaging (MRI) or bone scan confirmed by X-ray), prompted by symptoms is considered disease progression and should be recorded as new lesions. If progression is uncertain, patients may continue on treatment until the next scheduled assessment (ie, 8 weeks later +/- 1 week) or may have an unscheduled assessment earlier than this if considered appropriate by the investigator.

Lesions must be assessed using the same method and technique on each occasion. Lesions will be recorded on the pCRF page in the same order as they were recorded at screening. Details of any new lesions will also be collected. Response will be calculated in comparison to the baseline tumour measurements obtained before starting treatment. Progression will be calculated in comparison to when the tumour burden was at a minimum. Overall visit response will be recorded on the pCRF.

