4.4.2 Objective response rate (including RECIST)

4.4.2.1 Methods of assessment

Patients with measurable disease at baseline will be categorised using RECIST.

Patients with non-measurable disease at baseline will be assessed for CR, SD and PD.

Categorisation of overall visit response will be based on RECIST using the following response categories: CR, PR, SD, and PD (see [Appendix C](#)). In the case of stable disease,

measurements must have met the stable disease criteria at least once after randomization for a minimum interval of 6 weeks.

To be assigned a status of PR or CR, changes in tumour assessments must be confirmed no less than 4 weeks after the criteria for response were met.

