4.4.2.2 Derivation or calculation of outcome variable

Best overall response will be calculated as the best response recorded from date of randomisation (taking as reference for progressive disease the smallest measurements recorded since the treatment started) for each patient, and will be used for the summaries of objective response. Best overall response will be determined programmatically based on the RECIST criteria.

ORR is defined as the proportion of patients who have a best response of either CR or PR.

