5. CONFIRMATORY MEASUREMENT

5.1 Confirmation

To be assigned a status of PR or CR, changes in tumour measurements must be confirmed by repeat assessment that should be performed no less than 4 weeks after the criteria for response were first met.

In this study, the confirmation of response (CR or PR) it is determined by study protocol to be performed at next schedule visit.

In the case of stable disease, measurements must have met the stable disease criteria at least once after study entry at a minimum interval (in general, not less than 6–8 weeks).

For D1536C00001 study the interval defined in the study protocol is 8 weeks.

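### ORR and best response are summarised only in patients with a follow-up assessment, and, separately, the stable-disease minimum is 6 weeks in one section and 8 weeks in another

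*Protocol*

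**What the plan says.** **Who is counted.** Section 6.4.3.2 produces the BOR and ORR summaries by initial treatment, "for all patients from the safety population who have a baseline RECIST assessment and at least one follow-up RECIST assessment". Two other sections describe the endpoint differently. The exploratory objective in Section 2.3 is "Objective Response Rate (ORR; based on RECIST) for patients with measurable disease", with BOR restricted in the same way. Section 4.4.2.2 states that "ORR is defined as the proportion of patients who have a best response of either CR or PR", with no condition on follow-up.

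**When patients are assessed.** Tumour assessments are every 8 weeks from first dose. Section 4.4.1 adds that "Assessments may be performed +/- 7 days relative to the specified visit date" and that "patients who progress between scheduled visits should have a radiological imaging for confirmation". It also states: "Death will be regarded as a progression event in those patients who die before disease progression". CR and PR must be confirmed at least 4 weeks later (Section 4.4.2.1; Appendix C, Section 5.1).

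**Stable disease.** Section 4.4.2.1 requires that "measurements must have met the stable disease criteria at least once after randomization for a minimum interval of 6 weeks". Appendix C, Section 5.1 says: "For D1536C00001 study the interval defined in the study protocol is 8 weeks".

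**Status.** ORR and BOR are exploratory (Section 2.3) and nothing is formally tested (Section 6.4). Section 6.1 says that no separate SAP will be prepared because the protocol holds the full detail, so Section 6.4.3.2 is the rule that would be programmed.

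**The concern.** Requiring a follow-up assessment selects patients on something that happens after treatment starts. In a refractory population whose first scheduled scan is at Week 8, the patients without one are those who died, declined or stopped early. All of them are non-responders, so leaving them out can move the rate in one direction only. Summaries are by dose group, in cohorts of 6 to 9, where one or two missing patients visibly change a percentage.

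The population also departs from the objective. Patients with only non-measurable disease are eligible (Sections 3.3.2 and 4.4.3) and can be rated CR, SD or PD but not PR (Section 4.4.2.1). Section 6.4.3.2 does not exclude them.

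The stable-disease rule is a second, independent problem. BOR is to be derived programmatically (Section 4.4.2.2), and the programmer has two minimums to choose from. At stake is whether the preliminary efficacy description can be reproduced and compared fairly, not any decision within the trial.

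**Working it through.** The protocol gives no expected ORR, no sample size for ORR and no drop-out rate, so there is no figure of its own to reproduce.

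**1. Effect of the follow-up condition alone.** Let N be the dosed patients in the intended population, R the responders and d the share with no follow-up assessment. Confirmed CR or PR needs repeat assessments, so all R are among the N(1-d) patients who have them.

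- Rate in all dosed patients: R/N
- Rate under Section 6.4.3.2: R/[N(1-d)]
- Ratio: 1/(1-d), for any R above zero

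Assume d of about 5 to 30%, and take the planned maximum of about 70 patients (Section 3.1.1), treating all as measurable for illustration. Unscanned patients are whole numbers:

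| Unscanned | Scanned | Ratio | 4 responders (4/70 = 5.7%) | 7 responders (7/70 = 10.0%) |
|---|---|---|---|---|
| 4 (about 5%) | 66 | 70/66 = 1.06 | 6.1% | 10.6% |
| 7 (10%) | 63 | 70/63 = 1.11 | 6.3% | 11.1% |
| 14 (20%) | 56 | 70/56 = 1.25 | 7.1% | 12.5% |
| 21 (30%) | 49 | 70/49 = 1.43 | 8.2% | 14.3% |

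The specified output is by initial dose, so cohort figures are closer to what would be reported. With 1 responder:

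- Cohort of 6: 1/6 = 16.7%. With 1 or 2 unscanned, 1/5 = 20.0% or 1/4 = 25.0%.
- Cohort of 9: 1/9 = 11.1%. With 1 or 2 unscanned, 1/8 = 12.5% or 1/7 = 14.3%.

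**2. Effect of not restricting to measurable disease.** Against the objective's population, each unscanned measurable patient removes one from the denominator and each scanned non-measurable patient adds one. If no non-measurable patient has a CR, the two cancel when the counts are equal. Take a cohort of 6 with 5 measurable patients (1 unscanned, 1 responder) and 1 scanned non-measurable patient. The objective gives 1/5 = 20.0%. Section 6.4.3.2 gives 1/(4+1) = 20.0%, from a different set of patients.

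**3. Stable-disease minimum.** Week 8 is Day 57 in Table 1, which is 56 days after Day 1. With the 7-day window, on-time scans fall 49 to 63 days after first dose (7.0 to 9.0 weeks). The minimums are 6 x 7 = 42 days and 8 x 7 = 56 days. A stable scan at 49 to 55 days therefore meets the first and fails the second. ORR counts only CR and PR, so the choice changes ORR by zero. The two sections also start the interval at randomisation (this study has none) and at study entry respectively.

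**The case against.** A response-evaluable set is a familiar descriptive choice in a small Phase I trial, it is stated openly, and Section 6.4 lists all efficacy data by dose level, so exclusions can be traced. ORR and BOR are untested, and escalation rests on DLTs, PK and safety (Section 3.1.4.1). This stands, and it limits the importance of the point. It does not remove the mismatch with Sections 2.3 and 4.4.2.2, or the one-way effect of the follow-up condition.

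Several stronger readings are tempting, and the protocol does not support them:

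- **That all early failures vanish.** Section 4.4.1 asks for imaging when a patient progresses between visits. Those who are imaged stay in as PD.
- **That reported ORR must be inflated overall.** Only the follow-up condition is one-directional. Admitting non-measurable patients dilutes the rate, and the net effect depends on counts that are not given.
- **That the death rule flatly contradicts the denominator.** It defines progression and does not say who enters the summary. The tension is that an early death is a progression event in one section and absent from BOR in another.
- **That the two stable-disease minimums raise the response rate, or that about half of stable patients change category.** ORR does not use SD. Both rules ask for the criteria to be met at least once and scans repeat every 8 weeks, so a patient stable at Week 7 and again near Week 16 meets both.
- **That ORR is shown to look better at poorly tolerated doses.** Section 1.1.3 puts the mental-status events at 15 to 47 days after first dose, before the earliest on-time scan. It does not say how many of those patients had no later scan.

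**Conclusion.** The point holds as two separate, modest defects.

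First, the follow-up condition overstates any non-zero ORR by 1/(1-d) relative to the same population without that condition. The factor is about 1.06 to 1.43 for an assumed 5 to 30% unscanned. The direction follows from the confirmation requirement. The size rests wholly on the assumed d and the illustrative responder counts. Failure to restrict to measurable disease is a further departure from the objective that tends to pull ORR down, so the combined direction is not established.

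Second, the stable-disease minimum is contradictory. It affects patients whose only stable scan falls 49 to 55 days after first dose. It changes BOR categories and leaves ORR untouched, and the number of such patients cannot be derived from the protocol.

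Both are worth correcting, but neither bears on the primary objective, dose escalation or the MTD.

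**What to change.** - **Denominator (Section 6.4.3.2).** Use all dosed patients with measurable disease at baseline for ORR and BOR. Count patients without a follow-up assessment as non-responders, with BOR of PD if they died or progressed and not evaluable otherwise. Show the number unscanned per dose group.
- **Non-measurable disease.** Report these patients separately, using the CR, SD and PD categories.
- **Scanned-only rate.** Keep it as a labelled supplementary summary.
- **Stable disease (Section 4.4.2.1 and Appendix C, Section 5.1).** State one minimum in both places, counted from first dose, that an on-time scan within the 7-day window can meet. Either 6 weeks, or 8 weeks less 7 days (49 days), would do so.

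The cost is wording and programming, with no added visits or scans. With the other conditions unchanged, dropping the follow-up condition makes ORR slightly less favourable.
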